The additional monitoring may also help to direct normal postoperative care in terms of ventilatory support, the use of positive end-expiratory pressures, continued osmotherapy, and patient positioning. Finally, in postoperative patients with a neurological deficit or in those who must be maintained sedated or paralyzed, ICP- and brain tissue oxygenation (LICOX) with blood pressure monitoring are highly reliable methods to detect potential worsening as soon as possible. Of note, the infratentorial and supratentorial compartments are related by conduction of fluid in the subarachnoid space.

Under normal anatomical conditions, there is little intercompartmental difference in pressure between the infra- and supratentorial fossae. Surgery, brain shifts, or occlusion of the basilar cisterns may radically alter the equilibration of both compartmental pressures, since brain is a non-Newtonian fluid.³³ Furthermore, the pressure and compliance within the two compartments are different, as indicated by aforementioned studies.^{7-9, 12, 13, 25} A thorough review of the current literature reveals little information concerning the specific risks and complications related to direct posterior fossa monitoring, and just fractional knowledge of ICP pathophysiology in the posterior fossa and relations between both supra- and infratentorial compartments.

Ultimately, recent data^{1, 21, 23-26} strongly support the thesis that infratentorial monitoring is a safe technique, and most likely does not offer any greater risk than a subdural catheter located in the supratentorial space. In addition, the placement of the monitor within the operative site prevents exposing the patient to double jeopardy for infection, by avoiding a separate procedure. It is well known that the risk of infection is greatest at the time of introduction of any ICP monitoring device.

To summarize all intentions of the anticipated clinical trial we aim to:

- 1) prove the safety and feasibility of the intracranial multimodal monitoring in the posterior fossa,
- 2) establish the methodological use of infratentorial multimodal monitoring in patients with posterior fossa lesions as standard of care;
- 3) gain additional information of posterior fossa pathophysiology with complementary monitoring of the dynamical changes; subsequently

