- 4) facilitate the neurointensive care of these patients including ventilatory support, the use of positive end-expiratory pressures, continued osmotherapy, and patient positioning; ultimately
- 5) better understand of pathophysiological processes with
- 6) immediately identify of complications with subsequent prompt intervention if needed.

QUESTIONS

- * Is infratentorial multimodal neuromonitoring safe and feasible, and necessary?
- * Do data assessed by multimodal monitoring in the posterior fossa correlate with data from the supratentorial compartment?
- * Is infratentorial multimodal neuromonitoring able to timely predict complications such as local swelling, mass effect, vasospasm, ischemia, or infarction?
- * Is infratentorial multimodal neuromonitoring of value in daily clinical practice?

HYPOTHESES

- The intracranial multimodal monitoring in the posterior fossa is safe and feasible, without any increased risk due to additional probes.
- Data generated by infratentorial multimodal neuromonitoring do not completely correlate with data from standardized supratentorial multimodal neuromonitoring. There are significant differences in ICP- or brain tissue oxygenation values between the supratentorial and infratentorial compartments.
- The infratentorial multimodal monitoring immediately detects all relevant complications related to posterior fossa lesions including mass effect, local swelling, postoperative hematoma, ischemic events, decrease in the blood flow, vasospasm and inadvertent or prolonged vessel occlusion, or infarction, resulting in prompt therapeutic intervention if necessary.
- Additional information from infratentorial probes facilitate to maintain the critical patients including ventilatory support, the use of positive end-expiratory pressures, continued osmotherapy, and patient positioning.

CLINICAL RELEVANCE

Our prospective study can provide better guidance and optimization of clinical therapy through a comprehensive assessment of patients harboring posterior fossa lesions.

This study has very high potential to generate a new intellectual property, to yield discoveries improving the prediction of complications and monitoring the effects of treatments. The data will offer better understanding of pathophysiological mechanisms in posterior fossa lesions.

STUDY DESIGN

METHODS

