In phase I of the study 15 patients with posterior fossa lesions who require prolonged neurointensive care and in which any intracranial invasive intervention is indicated regardless of used technique or treatment modality will be enrolled in the study. The indication for posterior fossa lesion treatment will be decided on a case-by-case basis by our neurosurgical team irrespective of the study.

The study will start as a monocentric clinical trial (pilot study), and subsequently in phase II the study is planned to be continued as a multicentric trial.

In the majority of patients, ICP- and LICOX sensors are usually placed in the right frontal lobe and/or at the site of the lesion. In case of posterior fossa surgery, additional probes (ICP / LICOX) will be placed into the surgical field.

The neuromonitoring data will be recorded and analyzed. Additionally, demographic data, all treatment-related complications, and management of intracranial hypertension will be recorded.

All adverse effects will be noted and reported, even if no clinical consequence will ensue. Non-neurological complications such as cardiopulmonary complications will be documented separately.

After the invasive treatment of the posterior fossa lesion, all patients will undergo CT and/or MRI as standard of care within 72 hours after the intervention (the acute phase) as a protocol for detection of procedure-related complications. As standard of care, an additional follow-up MRI will be performed if needed. In stable patients a preoperative MRI will also be performed before invasive treatment

The following outcomes will be evaluated and analyzed: mean ICP, ICP pulse amplitude, respiratory waves, slow waves and the RAP (compensatory reserve) index of supra- and infratentorial ICP signals, transtentorial difference, brain tissue oxygenation, blood saturation, ASTRUP, and further vital parameters, peri- and postoperative morbidity and mortality, procedure-related morbidity including infection, hematomas, epilepsy, cerebral puncture, cranial nerve palsies, and CSF leaks, perioperative cerebral ischemia, long-term neurological morbidity and mortality, and overall neurological outcome.

Institutional review board will be obtained by the Ethics Committee of the Medical University Innsbruck, Austria. Informed consent will be acquired from all patients for participation in the study during the study period according to local requirements.

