Informed consent will be acquired from all patients for participation in the study during the study period.

All interventions and neuroimaging (e.g. MRI) will be performed as a part of routine clinical care and no modifications will be introduced in the treatment or the follow-up modalities currently used by the Department of Neurosurgery / Neuroradiology, except ^{31}P -MRS (see above).

CALCULATION OF THE NUMBER OF CASES

The study is designed as a prospective clinical trial (the sample of 30 patients was selected according to epidemiologic data and estimated annual incidence of posterior fossa lesions in Central Europe).

Regarding the complex patient cohort a high drop-out rate for MRI in the acute phase due to unstable patients with a consecutive infeasibility of MRI is to be expected.

ANALYSIS

Data collection

Clinical and procedural data will be collected prospectively. The adverse events are classified in three groups, according to their mechanism:

- * Lesion-related events
- * Intraoperative / intraprocedural (iatrogenic) events
- * Device-related problems

The outcome of adverse events is classified in four groups:

- * No clinical modification
- * Transient deficit(s)
- * Permanent deficit(s) (deficit(s) remaining at the 6-months follow-up)
- * Death

All-cause morbidity is defined as a modified Rankin score ≥ 3 . When the preoperative mRS was greater than 2, the all-cause morbidity is defined as any increase in the mRS value.

STATISTICAL ANALYSIS

The distribution of continuous variables will be described by using means and standard deviations, and discrete variables will be described as frequencies, percentages, and confidence intervals. The Clopper-Pearson exact method will be used to construct 95% confidence intervals (CIs).

The characteristics of both treatment groups will be compared by using Chi² test. All outcome results will be compared between the study groups by using a MannWhitneyU test, or Student t test where appropriate. P <0.05 is considered indicative of a statistically significant difference.

LITERATURE - REFERENCES

1. Mizunari T. [Clinical aspects and intracranial pressure monitoring in cases of traumatic posterior fossa hematoma]. *Nihon Ika Daigaku zasshi* 1990;57:334-343
2. Schroder R. [Expansive processes in the posterior cranial fossa and changes in intracranial pressure during the preoperative and postoperative period]. *Ceskoslovenska neurologie a neurochirurgie* 1982;45:306-314

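### The safety aim and hypothesis claim more than this pilot can show: no comparator, margin or acceptable rate is defined, and zero events still leave an upper 95% limit of 21.8% (n=15) or 11.6% (n=30)

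*Combined protocol and SAP*

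**What the plan says.** All references are to the combined protocol and SAP.

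- **Aims of the Study.** The first listed aim is to "prove the safety and feasibility of the intracranial multimodal monitoring in the posterior fossa".
- **Hypotheses.** The first reads: "The intracranial multimodal monitoring in the posterior fossa is safe and feasible, without any increased risk due to additional probes".
- **Study Design, Methods.** The design is a single-centre pilot: "In phase I of the study 15 patients with posterior fossa lesions" are to be enrolled, and "subsequently in phase II the study is planned to be continued as a multicentric trial". On probes, "ICP- and LICOX sensors are usually placed in the right frontal lobe and/or at the site of the lesion", and "In case of posterior fossa surgery, additional probes (ICP / LICOX) will be placed into the surgical field". The outcomes include "procedure-related morbidity including infection, hematomas, epilepsy, cerebral puncture, cranial nerve palsies, and CSF leaks". All adverse effects are to be recorded, even those without clinical consequence, and all patients have CT and/or MRI within 72 hours.
- **Calculation of the Number of Cases.** Here "the sample of 30 patients was selected according to epidemiologic data" and on estimated incidence. No event rate, precision target or power is given, and the 30 is not tied to a phase.
- **Analysis, Data collection.** Adverse events are grouped by mechanism as lesion-related, intraoperative or intraprocedural, or device-related. The grouping does not ask which probe was involved.
- **Statistical Analysis.** Proportions get exact 95% Clopper-Pearson intervals. Outcomes are compared between study groups at P<0.05, but no section says what those groups are.

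**The concern.** A claim of no increased risk from an added device is comparative. To support it, a study needs patients without the device, or an external rate with a margin, or at least a complication rate fixed in advance as acceptable. The plan has none of these. Its only inferential rule is a difference test, and failing to find a difference in a small sample is weak evidence that there is none.

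What the plan can deliver is a complication proportion with an exact interval, and that interval is wide at either stated size. The stake is the conclusion. The second aim is to establish infratentorial monitoring as standard of care, so a result of few or no events, read against the wording of the first aim and hypothesis, would carry weight that it does not have.

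There is a second, smaller problem. One patient may carry a routine frontal sensor, a routine sensor at the lesion and an added sensor in the surgical field. If the record does not say which probe an event belongs to, some events cannot be assigned to the probe under study.

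**Working it through.** **Inputs.** n=15 (Study Design, Methods); n=30 (Calculation of the Number of Cases); 95% Clopper-Pearson (Statistical Analysis). The plan does not say whether the interval is one- or two-sided. Two-sided is the usual reading, and both are shown. The plan states no upper limit or precision figure, so there is no figure of its own to reproduce.

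**Step 1: zero events.** The two-sided upper limit is 1 − 0.025^(1/n).
- n=15: 1 − 0.025^(1/15) = 0.218, or 21.8%.
- n=30: 1 − 0.025^(1/30) = 0.116, or 11.6%.

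The one-sided upper limit, 1 − 0.05^(1/n), is 18.1% at n=15 and 9.5% at n=30.

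**Step 2: other event counts.** For x events, the lower limit is the 2.5% quantile of Beta(x, n−x+1) and the upper limit is the 97.5% quantile of Beta(x+1, n−x).

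| Events | n=15 | n=30 |
|---|---|---|
| 0 | 0 to 21.8% | 0 to 11.6% |
| 1 | 0.2% to 31.9% | 0.1% to 17.2% |
| 3 | 4.3% to 48.1% | 2.1% to 26.5% |

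**Step 3: how often zero events would be seen anyway.** The probability is (1−p)^n. The documents give no rate for this endpoint, so p is an assumed range.

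| True rate (assumed) | n=15 | n=30 |
|---|---|---|
| 5% | 46.3% | 21.5% |
| 10% | 20.6% | 4.2% |
| 15% | 8.7% | 0.76% |

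With 15 patients, a true rate of 10% would go unseen about one time in five.

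**Step 4: the denominator.** Enrolment does not depend on treatment technique, but added probes go in only when there is posterior fossa surgery. Probe recipients may therefore number fewer than 15 or 30. Since 0.025^(1/n) falls as n falls, every zero-event limit above is then a minimum.

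**Step 5: the comparator.** The hypothesis concerns risk added by the extra probes. Methods describes no patients set aside without them and no allocation. Statistical Analysis names groups but does not define them, so no two-group calculation is offered here. The planned multicentre phase has no size tied to it and no safety criterion, so it does not supply what is missing.

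**Step 6: attribution.** Imaging within 72 hours may place a hematoma near a frontal or a posterior fossa probe. It will not generally do so for an infection or a CSF leak. Because routine sensors may themselves lie at a posterior fossa lesion, site alone would not separate routine from added probes.

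**The case against.** The best defence is that Methods calls this a pilot, plans to record every adverse effect, and already specifies exact intervals. On that view the word prove is loose drafting, and the analysis will show its own uncertainty. This stands in part. The study can reasonably estimate complications and assess feasibility, and nothing here argues against running it. But a pilot label does not make the two statements supportable, and they are the ones against which results will be read.

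A second objection is that the number 30 may be the total or may belong to the second phase. That is fair: the text does not say. Both sizes are therefore shown, and the conclusion is the same for each.

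Some stronger readings are tempting but not supported:
- A reader might infer that device events cannot be attributed to a probe at all. Early imaging and full adverse-event recording make that too strong, and grouping by mechanism does not exclude noting location.
- A reader might infer that the plan commits to reporting zero events or a non-significant test as proof. It states no safety decision rule; it simply does not rule that reading out.
- A reader might use the 1.1% to 7.7% quoted in the Present section as a limit that the study fails to meet. That range is background for ICP monitoring in general, not an acceptance threshold.

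**Conclusion.** The concern holds. As worded, the safety part of the first aim and first hypothesis cannot be established by this phase. There is no comparator, margin or acceptable rate, and zero events would still be compatible with a complication rate of up to 21.8% (n=15) or 11.6% (n=30). Read one-sided, the limits are 18.1% and 9.5%, and the conclusion does not change. The figures assume that every enrolled patient receives an added infratentorial probe; with fewer recipients the limits rise.

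The attribution gap is real but partial: events such as infection or CSF leak may not be separable between added and routine probes, whereas a hematoma may be localised by imaging.

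The limits describe how little a small sample can exclude. They are not evidence that the probes are unsafe. The wording should be corrected before results are known; data collection need not wait.

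**What to change.** 1. **Restate the safety part and keep the feasibility part** of the first aim and first hypothesis. Suggested text: to estimate, among patients who receive an added infratentorial probe, the proportion with at least one new complication after probe placement from the procedure-related list in Methods, with an exact 95% Clopper-Pearson interval. The period should be the one over which adverse events are already recorded, written out explicitly. The 6-month point in the plan serves only to define a permanent deficit. Report deaths and losses to follow-up alongside.
2. **State the precision and its limits in advance.** Include the intervals for 0, 1 and 3 events from the first table above, and say which phase the 30 refers to. State that the proportion includes complications of the lesion and the operation and is not an excess risk. State that neither zero events nor a non-significant test will be reported as proof of safety or of no increased risk.
3. **Record the probe.** For device-related and procedure-related events, add probe role (added or routine) and probe site (infratentorial or supratentorial), with a not-attributable option. Report these descriptively, without a test between probes.

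**Cost.** The safety conclusion becomes more modest, the reported proportion will be higher than a probe-specific rate would be, and the form gains two fields. No extra patients or procedures are needed.

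### The first sentence of the second hypothesis cannot be refuted, and no planned analysis shows whether the two compartments agree within patients

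*Combined protocol and SAP*

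**What the plan says.** In the combined protocol and SAP, QUESTIONS frames the comparison of compartments as correlation: "Do data assessed by multimodal monitoring in the posterior fossa correlate with data from the supratentorial compartment". The second entry under HYPOTHESES answers in two sentences. The first is that the infratentorial data "do not completely correlate with data from standardized supratentorial multimodal neuromonitoring". The second is more specific: "There are significant differences in ICP- or brain tissue oxygenation values between the supratentorial and infratentorial compartments". Neither gives a coefficient, a threshold or a difference that would matter clinically.

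The outcome list under METHODS includes "supra- and infratentorial ICP signals, transtentorial difference, brain tissue oxygenation", so a quantity on the difference scale is to be evaluated. No method or margin is attached to it.

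STATISTICAL ANALYSIS provides means and SDs, frequencies, Clopper-Pearson intervals and a Chi² test. It then states: "All outcome results will be compared between the study groups by using a MannWhitneyU test, or Student t test where appropriate", with "P <0.05 is considered indicative of a statistically significant difference". It names no correlation coefficient, no paired analysis and no agreement method.

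**The concern.** The PRESENT section treats it as an open question whether a supratentorial monitor reflects what happens in the posterior fossa, and it cites an animal model that found no relevant gradient. Both answers are therefore possible, and the study should be able to give either. A sentence that asserts only imperfect correlation will be borne out whatever the compartments do. Correlation is also the wrong quantity for a pressure gradient, since two signals a fixed distance apart correlate perfectly.

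Among the stated aims is to establish infratentorial monitoring as routine care. A report that the first sentence was confirmed would lend support to that aim without carrying information. A non-significant mean difference, in turn, could be misread as showing that one monitor can stand in for the other.

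**Working it through.** The documents give no correlation threshold, SD, margin or power for this hypothesis, so there is no planned figure to reproduce. The sample sizes are theirs: "In phase I of the study 15 patients with posterior fossa lesions" under METHODS, and "the sample of 30 patients was selected according to epidemiologic data and estimated annual incidence" under CALCULATION OF THE NUMBER OF CASES. Both n=15 and n=30 are used below. The SDs, error sizes and offsets are assumptions for illustration.

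**1. Can the first sentence fail?** Suppose both compartments have the same true pressure, with between-patient SD 5 mmHg and independent probe error of SD e. The expected correlation is r = 25/(25 + e²):

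- e = 1: 25/26 = 0.96
- e = 2: 25/29 = 0.86
- e = 3: 25/34 = 0.74

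In 4,000 simulated studies at each sample size, with identical true pressures and e = 0.5 or 1, the sample r was below 1 in 100% of runs. The exact values depend on the assumptions; r < 1 under any independent error does not.

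**2. Does r detect an offset?** With e = 0.5, the median r was about 0.99 with no offset and about 0.99 with a constant 8 mmHg offset.

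**3. Can the second sentence fail?** Yes. With no true difference, a paired t test at 0.05 was significant in 4% to 5% of simulated studies, and an independent-samples t test in about 0%. If significance on either ICP or oxygenation counts, the chance of a false positive is 1 − 0.95² = 9.75% for two independent tests.

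**4. Does a test of mean difference measure agreement?** No. Take 30 patients, 15 with infratentorial ICP 10 mmHg higher and 15 with it 10 mmHg lower. The mean difference is 0, so the test finds nothing. The SD of the differences is 10·√(30/29) = 10.2 mmHg and the limits of agreement are about ±1.96 × 10.2 = ±20 mmHg. The monitors disagree in every patient. Nor does non-significance show agreement: a paired test has 80% power only for a mean difference of 0.78 SD at n=15 or 0.53 SD at n=30.

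**5. What precision would an agreement analysis have?** Take one summary difference per patient, in units of the SD of the differences:

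- Mean difference, t(0.975, n−1)/√n: 2.145/√15 = 0.55; 2.045/√30 = 0.37.
- Each limit, t(0.975, n−1)·√(1/n + 1.96²/(2(n−1))): 2.145 × 0.4515 = 0.97 at n=15; 2.045 × 0.3155 = 0.65 at n=30.

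**6. How much of the limits is probe error?** With identical true pressures, error alone gives limits of ±1.96·√2·e: ±2.8, ±5.5 or ±8.3 mmHg for e = 1, 2 or 3. A margin set below these values would declare discordance from noise.

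**The case against.** A reader might infer that the whole second hypothesis is confirmed by any result, or that no data from this study could show the compartments to be alike. The documents do not support that. The sentence on significant differences belongs to the same hypothesis and can come out negative, as step 3 shows, and the transtentorial difference is a listed outcome. The example of a constant gap is also largely covered by that sentence: a fixed offset is what a test of differences looks for. The plan does not rest on correlation alone.

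It can also be said that correlation may be meant as tracking over time within a patient. The outcomes include slow waves, pulse amplitude and the RAP index, and the stated goal concerns dynamic changes. For that purpose a fixed offset is no contradiction, and asking about tracking is legitimate. This stands, but the plan does not say which correlation is meant, names no method for it, and still sets no value at which the statement would fail.

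Finally, the study starts as a pilot, and no named primary endpoint depends on this sentence. That limits the consequence. It does not remove the gap between the question asked and the analyses listed.

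**Conclusion.** The concern holds for the first sentence of the second hypothesis and for the missing agreement analysis; it does not extend to the hypothesis as a whole. The first sentence is true whenever there is independent measurement error, and correlation cannot reveal a constant offset; neither conclusion depends on the assumed SDs. The second sentence is refutable, but it has no relevant difference, no stated paired method and no rule for the alternative between ICP and oxygenation. A test of means would not, in any case, answer whether the two monitors agree in individual patients.

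The illustrative correlations (0.96, 0.86, 0.74) rest on an assumed between-patient SD of 5 mmHg and probe error SD of 1 to 3 mmHg. The precision figures assume one summary difference per patient and roughly normal differences. This should be corrected, at small cost.

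**What to change.** Under HYPOTHESES, replace the first sentence with a statement that data could contradict, phrased as agreement between compartments within a stated margin. Under STATISTICAL ANALYSIS, add:

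- The within-patient supratentorial-minus-infratentorial difference in ICP and in brain tissue oxygenation, with its mean and 95% CI, and the 95% limits of agreement with their own CIs.
- One summary value per patient, or a method that allows for repeated readings within patients.
- A margin for each variable, fixed by the sponsor before the first patient and set with probe error in mind, and a statement of whether the limits themselves or their confidence bounds must exceed it for the compartments to be called discordant.
- If tracking over time is of interest, a separate analysis of it, not reported as agreement.
- The expected precision: ±0.55 SD (n=15) or ±0.37 SD (n=30) for the mean difference, and about ±0.97 or ±0.65 SD for each limit.

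The cost is wording in two sections; the measurements are already planned. The sponsor must commit to a margin in advance. The limits will be imprecise at n=15: a half-width of 0.97 SD is about half the 1.96 SD distance between a limit and the mean.

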In the past, recording of ventricular fluid pressure has proved to be a reliable method in clinical neurosurgery, as shown by Lundberg et al.¹⁸⁻²⁰ Furthermore, some authors recorded supratentorial pressure during posterior fossa surgery with the intention of obtaining continuous information on the pressure state in major intracranial compartment.^{3, 21, 22}

Of note, some surgeons were reluctant to introduce direct subdural posterior fossa monitors for a number of reasons. Some of the possible problems may include cerebrospinal fluid (CSF) leaks, cranial nerve dysfunction, and the possibility of brainstem irritation with resulting autonomic dysfunction. Yet, many recent studies have showed the safety and feasibility of intracranial monitoring in the posterior fossa.^{1, 21, 23-26}

PRESENT

With regards to pathophysiology and clinical practice, the intracranial pressure (ICP) profiles in the supratentorial and infratentorial compartments remain unclear. After a neurosurgical operation in the posterior fossa there are most likely pressure differences between supra- and infratentorial spaces.²⁷ It is well known that the pressure within the skull is unevenly distributed, with demonstrated ICP gradients.²⁵ By contrast, Rieger et al²³ reported no significant differences between supratentorial and infratentorial ICP values in an animal model. The infratentorial ICP elevation in the presented pig model led to a uniform ICP elevation in the intracranial space without development of a considerable pressure gradient below and above the tentorium. Importantly, in the low pressure part of the ICP curve, cerebrospinal fluid connects the compartments and contributes to the pressure equilibrium.

To rely on autonomic changes or neurological deterioration as signs of a postoperative complication narrows the temporal margin of safety for the institution of treatment.

It has been the policy of our Department to electively monitor all complex posterior fossa procedures via a supratentorial intracranial multimodal monitoring; however, it remains unclear whether an acute change in the posterior fossa would be reflected by the supratentorial monitor prior to clinical deterioration.

Thus, we intend to apply the intracranial multimodal monitoring in both infratentorial and supratentorial compartments simultaneously. Such coincident measurements most likely will be the most sensitive way to assess focal swelling, ischemia and tissue perfusion in the posterior fossa structures.

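### The study sets out to test detection, but no planned analysis links probe signals to complications, and the claim that the probe detects all of them can only be an estimate

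*Combined protocol and SAP*

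**What the plan says.** The section on the aims of the study opens with a comparative goal: to test whether monitoring below the tentorium is better at picking up change in the compartment operated on. It adds immediate detection of complications as an aim. The Questions section asks: "Is infratentorial multimodal neuromonitoring able to timely predict complications such as local swelling, mass effect, vasospasm, ischemia, or infarction". The third entry under Hypotheses goes further: "The infratentorial multimodal monitoring immediately detects all relevant complications related to posterior fossa lesions including mass effect", followed by a list of other complications and "resulting in prompt therapeutic intervention if necessary".

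The layout is paired. Under Present the protocol says "we intend to apply the intracranial multimodal monitoring in both infratentorial and supratentorial compartments simultaneously". Methods lists outcomes that include "slow waves and the RAP (compensatory reserve) index of supra- and infratentorial ICP signals, transtentorial difference", together with oxygenation values and clinical morbidity. Variables and Parameters adds the occurrence of lesion-related complications. Methods also provides CT and/or MRI within 72 hours of the intervention.

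Statistical Analysis offers descriptive summaries, Clopper-Pearson 95% intervals, a Chi-square test of characteristics between two treatment groups, and Mann-Whitney U or Student t tests of all outcomes between study groups. Neither grouping is defined anywhere.

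Two sizes appear. Methods states "In phase I of the study 15 patients with posterior fossa lesions"; the section on the number of cases gives 30, based on incidence.

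**The concern.** Detection is a relation between two records: what a probe showed, and what happened to the patient and when. The plan collects much of both but never joins them. It has no definition of an alarm, no rule for matching an alarm to a complication, and no count of alarms without a complication.

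With these rules open, whether the hypothesis was met would be decided after the data are seen. A short run of complications without a miss could be reported as complete detection although the probe misses a material share. Phase I is a pilot for a multicentre phase II, so such a reading would carry forward into the design of the larger trial.

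**Working it through.** **Step 1. Does any planned analysis reach detection?**

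- *Transtentorial difference and signal indices (Methods).* These contrast values between compartments and serve the second hypothesis, on differences and correlation. They do not record whether a probe flagged an event.
- *Occurrence of complications (Methods; Variables and Parameters).* Events are recorded. Under Data collection, adverse events are classed by mechanism and outcome, not by onset time or by what revealed them.
- *Chi-square, Mann-Whitney U, Student t (Statistical Analysis).* As named, these are tests for independent groups. The two probes are in the same patient, so even if the groups meant the compartments, the pairing would be lost and there would still be no detection variable to test.
- *Clopper-Pearson intervals (Statistical Analysis).* These could carry a sensitivity estimate, but no numerator or denominator is defined.
- *Imaging within 72 hours (Methods).* It can confirm a complication. It is not tied to the signals, does not time onset and does not exclude later events.
- *Monitoring details (Intervention/Examination).* These are referred to another study's protocol, which is not available here. This plan ties no threshold from it to an analysis.

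**Step 2. What could a run without a miss show?**

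The plan states no sensitivity, event rate, power or precision target, so it has no figure of its own to reproduce. The inputs from the documents are 15 and 30 patients and the exact 95% interval. The documents give no rate for lesion-related complications; the 1.1% to 7.7% quoted before the aims concerns complications of ICP monitoring itself. Event counts of 3, 6 and 9 are therefore assumptions (10%, 20% and 30% of 30 patients, or 20%, 40% and 60% of 15). The true sensitivities of 80% and 90% are also assumptions.

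With k of k complications detected, the lower limit solves p^k = 0.025, so it equals 0.025^(1/k). The chance of no miss at true sensitivity s is s^k.

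| Complications k, all detected | Lower 95% limit | Chance of no miss, s = 80% | Chance of no miss, s = 90% |
|---|---|---|---|
| 3 (assumed) | 29.2% | 51.2% | 72.9% |
| 6 (assumed) | 54.1% | 26.2% | 53.1% |
| 9 (assumed) | 66.4% | 13.4% | 38.7% |
| 15 (one per phase I patient) | 78.2% | 3.5% | 20.6% |
| 30 (one per patient) | 88.4% | 0.1% | 4.2% |

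Example: 0.025^(1/15) = 0.782, so 15 of 15 leaves a miss rate of up to 21.8% not excluded.

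**Step 3. What could a paired comparison of probes show?**

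The exact two-sided McNemar P value, with all d discordant patients in one direction, is 2 × 0.5^d: 0.0625 for d = 5 and 0.031 for d = 6. Fewer than 6 discordant patients cannot reach the plan's 0.05 (sidedness is not stated; two-sided is assumed). At these sizes the test can be descriptive only.

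**Step 4. How many patients can contribute?**

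Enrolment covers patients in whom "any intracranial invasive intervention is indicated regardless of used technique or treatment modality will be enrolled in the study". Infratentorial placement is narrower: "In case of posterior fossa surgery, additional probes (ICP / LICOX) will be placed into the surgical field". The frontal or lesion-site sensors are described as usual in most patients, not universal. Either probe may therefore be absent, and the paired denominator may fall below the number enrolled.

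**The case against.** The strongest reply is that this is a pilot, that no finite sample ever proves a claim about all events, and that the raw data are largely collected already. All three stand. They make this a matter of definitions, analysis and wording, and they argue for estimation over a powered test. They do not supply the missing link between signals and events.

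Several stronger readings are tempting but not supported:

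- A reader might infer that the third hypothesis itself compares the two probes. It concerns the infratentorial probe alone; the comparison is in the goal stated under the aims.
- A reader might take 78% and 88% as the most that 15 or 30 patients could yield. They hold when one complication is counted per patient. The protocol names several types and a patient may have more than one, though further events would be clustered.
- A reader might infer that treating flagged events must lower apparent sensitivity by a calculable amount. The documents do not allow this. Methods records adverse effects even when nothing clinical follows, as well as the management of intracranial hypertension, and one outcome class covers events without clinical change. A treated event may thus still be counted; only one that never arose is lost.
- A reader might treat detection as a minor aim because it comes last in the numbered summary. The opening goal contradicts that.

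It is also fair to object to a single alarm rule for both probes. The protocol itself says that pressure and compliance differ between the compartments, so the definitions may need to differ.

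**Conclusion.** The point holds. Followed as written, the plan cannot answer its comparative detection goal, its question on timely prediction or its third hypothesis, because no analysis connects signals to recorded complications and the named tests do not fit paired probes.

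The size depends on the number of complications, which the documents do not give. At the assumed 3 to 9 events, a perfect record is compatible with a true sensitivity as low as 29% to 66%, and a probe with an assumed sensitivity of 80% would produce that record in 51% to 13% of studies. At one event per patient in 15 or 30 patients, a perfect record would be unlikely with such a probe (3.5% and 0.1%), but the lower limits of 78% and 88% would still fall short of complete detection. These figures assume independent events and one counted event per patient.

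This should be corrected before the data are reviewed. It is not a reason to enlarge or power the pilot.

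**What to change.** 1. Restate the third hypothesis as estimation of sensitivity, for planning phase II.
2. Before data review, have the investigators fix an analysis-only alarm definition and matching window for each probe. Definitions may differ by compartment, must be set without reference to the complications, and do not guide care.
3. In patients with usable data from both probes, take the first confirmed complication during monitoring. In place of the unpaired group tests, report counts detected by the infratentorial probe only, the supratentorial probe only, both and neither, with each probe's sensitivity and the Clopper-Pearson interval already planned. Exact McNemar is descriptive only. List further events descriptively and note the clustering.
4. Report unmatched alarms per monitored day for each probe. Show separately the alarms followed by an intervention, because treatment may alter whether an event appears.
5. Report lead time only where onset is known, and state that the scan within 72 hours neither times onset nor rules out later events.
6. State how many patients have both probes.

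The cost is analyst time for matching and artefact handling, one event-time field on the case report form, and revised wording. The resulting claim is weaker, with wide intervals, and onset will stay unknown for some events. No added patients or imaging are needed.
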